2.2 Objectives and Purpose

The goal of this study is to determine the effectiveness of Liposomal bupivacaine at reducing opioid consumption from 24-72 hours when used along with Bupivacaine 0.5% for single shot ISB for total shoulder arthroplasty. In addition, we would also like to determine if Liposomal bupivacaine is effective at prolonging the sensory block and reducing post-operative pain in patients after TSA surgery. We would also

CONFIDENTIAL

This material is the property of the NYU School of Medicine and Langone Medical Center. Do not disclose or use except as authorized in writing by the study sponsor

like to determine how reduction in post-operative pain impacts a patient’s hospital stay in the short term. Primary outcomes measures will be opioid utilization (in morphine milligram equivalents [MME]) during a 72-hour post-operative period. Secondary outcomes include patient reported pain scores, VAS. While it is expected that the greatest benefit of Liposomal bupivacaine plus Bupivacaine 0.5% will be seen within 24-72 hours after surgery, it is possible that there will be in an overall reduction in long-term opioid use (up to 4 weeks). Secondly, function/rehabilitation, length of stay, and complications may be impacted by combined use of Liposomal bupivacaine plus Bupivacaine 0.5%.

3 Study Design and Endpoints

ARM 1: Experimental	Sample Size: 92	10 mL Bupivacaine 0.5% + 10 mL Liposomal Bupivacaine
ARM 2: Control	Sample Size: 92	20 mL Bupivacaine 0.5%

3.1 Description of Study Design

PRE-SCREENING PHASE/CONSENTING PHASE:

Surgeons will inform eligible patients of the study during their pre-surgical visit in their office. The surgeons will use an IRB-approved recruitment flyer to help explain the study to the eligible patient. If the patient is agreeable, a member of the research team will provide further details and ask the patient to participate on day of surgery. Informed consent will be obtained on DOS when the patient is in the pre-operative holding room by an authorized research member.

BASELINE ASSESSMENTS:

After informed consent has been obtained, participants will complete a total of 3 PROMIS assessments (Upper Extremities, Pain Intensity and Global Physical Health) before undergoing their TSA surgery.

RANDOMIZATION PHASE:

Subjects scheduled to undergo TSA will be randomized to either the Bupivacaine 0.5% plus Liposomal bupivacaine Or Bupivacaine 0.5% group. Randomization of each subject will be done on day of surgery using randomization.com software to generate the assignment.

TREATMENT PHASE:

Subjects in the Bupivacaine plus Liposomal bupivacaine group will receive an interscalene nerve block with 10mL 0.5% Bupivacaine and 10mL of Liposomal bupivacaine. The control group will receive an interscalene nerve block with 20mL 0.5% Bupivacaine HCL. The anesthesiologist will NOT be blinded to what solution is being injected, as liposomal bupivacaine is a white fluid while bupivacaine is clear. All other stakeholders (patient, surgeon, other caregivers, and research staff collecting the data) will be blinded to the patient’s group assignment.

POST-OPERATIVE PHASE:

After initial recruitment, subjects’ pain will be assessed via visual analog scale (VAS) by nursing staff during the post-operative period as per standard of care. The VAS pain scores are collected and documented in the patient’s electronic medical record. Additionally, a standardized regimen of pain medication will be given to all subjects who are enrolled. The pain medications given to patients are standard of care medications and vary based on pain level. The clinical staff determines this for each patient.

CONFIDENTIAL

This material is the property of the NYU School of Medicine and Langone Medical Center. Do not disclose or use except as authorized in writing by the study sponsor

Occupational and physical therapy progress and activity goals will be reviewed. As per standard of care, motor testing of the operated shoulder and arm will be assessed during these visits. This includes: No weight bearing exercises will be performed as per surgeon's instructions and the nursing staff will continue to obtain VAS pain scores.

[figure not shown]
During the 24-72 hour post-operative period, research staff will visit the patient while they are in the hospital to obtain and verify the pain medication taken. If the patient is discharged before the 72-hour period, the research staff will give the patient a copy of a medication record diary to complete. Additionally, the staff member will call the patient within 1-2 business days to obtain the remaining opioid utilization information.

After discharge, the research staff will continue to follow up with the patient on POD 7, POD 14 and POD 30 to assess pain scores, opioid usage patterns, and functional status. The pain intensity PROMIS assessment will be administered during each phone call. Additionally, on POD 30, participants will complete the Upper Extremity PROMIS form. Research staff will verify documented opioid refills through Epic and pharmacy records.

CONFIDENTIAL

This material is the property of the NYU School of Medicine and Langone Medical Center. Do not disclose or use except as authorized in writing by the study sponsor

3.2 Schematic of Study Design

CONFIDENTIAL

This material is the property of the NYU School of Medicine and Langone Medical Center. Do not disclose or use except as authorized in writing by the study sponsor

4 Study Enrollment and Withdrawal

The researchers will approach patients scheduled for primary total shoulder arthroscopy who are eligible for participation in the study. Anesthesiology attendings, fellows, residents and authorized researchers will consent and enroll patients pre-operatively.

4.1 Inclusion Criteria

1. Patients between 18 and 85 years of age
2. Patients undergoing total shoulder arthroplasty; and
3. Patients who consent to be randomized.

4.2 Exclusion Criteria

1. Patients younger than 18 and older than 85;
2. Patients with a history of chronic pain that have used opioids for pain management for 3 months or longer;
3. Patients who are allergic to oxycodone;
4. Patients who are unable to speak English;
5. Patients with diagnosed or self-reported cognitive dysfunction;
6. Patients with a history of neurologic disorder that can interfere with pain sensation;
7. Patients with a history of drug or recorded alcohol abuse;
8. Patients who are unable to understand or follow instructions;
9. Patients with severe liver disease, renal insufficiency, congestive heart failure, and/or significant heart disease;
10. Patients with an allergy or contraindication to any of the medications used in the study, or patients with a contraindication to any study procedures;
11. Patients with BMI over 40;
12. Any patient that the investigators feel cannot comply with all study related procedures;
13. NYU Langone Health students, residents, faculty or staff members

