6.2 Analysis of Endpoints

Primary Endpoints:

Opioid utilization (expressed as oral morphine mg equivalents) used during initial 24-72 hours post-operative period after surgery.

Secondary Endpoints:

CONFIDENTIAL

This material is the property of the NYU School of Medicine and Langone Medical Center. Do not disclose or use except as authorized in writing by the study sponsor

Duration of opioid use
Patient reported pain scores (VAS)
Length of stay
Progress with physical therapy
Reported long-term narcotic use at home
Discharge location: home, acute rehab or skilled nursing facility
Documented opioid refills
Adverse events such as respiratory depression, hypoventilation, reintubation, nausea, constipation

The analysis of opioid use, VAS, and PROMIS assessments will rely on a univariate analysis of variance model for mean score. This model is in the class of models commonly known as unirep-ANOVA models. It assumes that the mean score is a function of elapsed time and the treatment regimen assigned. This model considers the fact that the subject's repeated measures are correlated. The fitted model will provide statistical estimates of the mean levels, the treatment-effect differences between mean levels, the standard deviation, the intra-class correlation coefficient, 95% CIs, standard errors (SE), and statistical hypothesis tests. The estimates of means will be used to compute summary criteria such as area under the curve (AUC) for each regimen. All estimates reported will be presented their 95% CIs.

All endpoints will be evaluated as fits the data set with graphical figures such as scatter plots, box-and-whisker plots, and frequency histograms to visualize the distribution of these outcomes and their relationships to covariates and treatment assignment. When appropriate descriptive graphical and tabular methods will also be estimated and presented in a graphical figure.

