6.2.1 Baseline Descriptive Statistics

The following patient data will be recorded: age, gender, height, weight, date of admission, date of discharge, laterality, surgical approach, implants used, duration of surgery, contamination, ASA, comorbidities (smoking, cardiac history, diabetes etc.), CBC (WBC, PCV, HGB, RBC, indices, platelet count, differential), and medications. All of this information will be accessible in the patient's medical record.

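### Patients still taking opioids at surgery can enter under the 3-month threshold, and the opioid analysis has no term for pre-operative use

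*Combined protocol and SAP*

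**What the plan says.** Exclusion 2 in Section 4.2 removes "Patients with a history of chronic pain that have used opioids for pain management for 3 months or longer". It requires both a chronic pain history and at least 3 months of opioid use. It sets no dose, no test of current use and no window before surgery.

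No other criterion deals with prescribed opioids before surgery. Exclusion 7 concerns "Patients with a history of drug or recorded alcohol abuse", and exclusion 12 concerns "Any patient that the investigators feel cannot comply with all study related procedures". The inclusion criteria in Section 4.1 do not ask for opioid-naive patients.

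The primary endpoint in Section 6.2 is "Opioid utilization (expressed as oral morphine mg equivalents) used during initial 24-72 hours post-operative period after surgery". The Protocol Summary and Section 2.2 give the window as the first 72 hours; the point below holds for either. The secondary endpoints include duration of opioid use, "Reported long-term narcotic use at home" and documented refills. None is limited to use that began with the surgery. Section 3.1 adds: "Research staff will verify documented opioid refills through Epic and pharmacy records".

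The Section 6.2 model for opioid use, VAS and PROMIS scores contains elapsed time and assigned treatment. Section 6.4 describes a generated allocation list for all 184 participants and names no stratification factor. Section 6.2.1 lists among the recorded patient data "comorbidities (smoking, cardiac history, diabetes etc.), CBC (WBC, PCV, HGB, RBC, indices, platelet count, differential), and medications". It does not single out opioids or say how the medication list will be used.

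**The concern.** Opioid consumption is the primary outcome, so opioid use just before surgery is close to a baseline measurement of the same quantity and is likely to be strongly prognostic. Left out of the model, the difference between users and non-users goes into the residual variance of the treatment comparison.

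The longer-term endpoints have a further difficulty. In someone already taking opioids, use at POD 30 or a refill in the pharmacy record may simply continue an older prescription. As the endpoints are defined, continuing use cannot be told apart from new use after surgery. That matters because Section 2.1 (Statistical Hypotheses) includes reduced opioid dependency and Section 2.2 raises the possibility of lower use up to 4 weeks.

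**Working it through.** **Who is eligible.** Take a patient who has used opioids daily for 10 weeks for the arthritic shoulder and still takes them on the day of surgery. Exclusion 2 does not apply, because 10 weeks is under 3 months. Exclusions 7 and 12 do not apply on these facts, and the inclusion criteria are met. The route in is the duration threshold. As written, a longer-term user with no chronic pain history is also eligible, though few patients are likely to fit that description.

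**Plan figures.** Section 4.6 gives 184 enrolled for 146 evaluable, an implied loss of 1 − 146/184 = 20.65%. At an assumed 20% loss, 73/0.8 = 91.25, rounded up to 92 per arm, or 184 in total, which agrees with the plan. The 146 cannot be reproduced, because Section 6.3 gives no alpha, power, effect size or SD. I use 146/2 = 73 evaluable per arm.

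**Assumptions not in the documents.** A share p of entrants takes opioids at surgery. Their mean outcome is d SD higher in both arms, where 1 SD is the spread within users and within non-users.

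**Variance without adjustment.** The outcome variance becomes 1 + p(1−p)d². The standard error is multiplied by the square root of that.

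| p | d | p(1−p)d² | Variance increase | SE multiplier |
|---|---|---|---|---|
| 0.1 | 0.5 | 0.1 × 0.9 × 0.25 = 0.0225 | 2% | √1.0225 = 1.011 |
| 0.2 | 1.0 | 0.2 × 0.8 × 1 = 0.16 | 16% | √1.16 = 1.077 |
| 0.3 | 1.5 | 0.3 × 0.7 × 2.25 = 0.4725 | 47% | √1.4725 = 1.213 |

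**Chance imbalance.** For p = 0.2, the difference between arms in the share of users has standard error √(2 × 0.16/73) = 0.066, which is 0.066 SD of outcome at d = 1. This is not an additional effect: 2/73 + 2(0.16)/73 = 2(1.16)/73, so it is already inside the 8% increase in standard error.

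**Power, for scale.** Assume two-sided alpha 0.05 and 80% power at 73 per arm if nobody used opioids before surgery. The detectable difference is then (1.960 + 0.842) × √(2/73) = 0.464 SD. Unadjusted power is Φ(2.802/SE multiplier − 1.960). In the order of the table this gives 79%, 74% and 64%. For the middle row, holding 80% would take 73 × 1.16 = 84.7, or 85 per arm.

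**Refills and POD 30 use.** At the extreme, every pre-operative user in both arms counts as an event whatever block was given. A risk difference of X among non-users then appears as (1 − p)X overall: 0.9X, 0.8X and 0.7X for p = 0.1, 0.2 and 0.3.

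**The case against.** Admitting shorter-term users is a legitimate choice that keeps the sample closer to the patients who have this operation. That stands, and it is why the criterion should be left alone. A rewording that kept the 3-month duration and added a look-back would still admit the 10-week user.

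A reader might infer that current users get in because exclusion 2 has no look-back. The text does not support this. A missing look-back widens the exclusion: read literally, it also removes someone whose 4 months of use ended 15 years ago. That costs some recruitment but distorts no outcome.

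A reader might also infer that the treatment comparison is biased. It is not: allocation is randomised 92 to 92, so users balance in expectation, and continuing use adds to both arms alike.

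It is also fair to say that the route into the primary endpoint is inferred. Section 3.1 describes a standardised regimen that varies with pain level, and nothing says a previous opioid continues alongside it. The statement must therefore be that continuing use can count, not that it will.

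Finally, Section 6.2 plans plots of outcomes against covariates, and the Protocol Summary lists linear regression. Neither names opioid use or prespecifies an adjustment, so this answers the point only in part. The strongest remaining objection is that p and d are unknown: at the low end the loss is trivial.

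**Conclusion.** The point holds as one of precision and interpretation. Eligibility as written admits current users with under 3 months of use, the opioid endpoints do not separate their continuing use from new use, and the stated model does not account for it although medications are recorded at baseline.

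The size rests wholly on assumed values. The middle case costs about 8% in standard error, or roughly 6 points of power from an assumed 80%. The assumed range runs from negligible to a 47% increase in variance. The difficulty in reading the refill and 4-week outcomes needs no particular d; it arises whenever some entrants are existing users. The documents support neither a claim of systematic bias nor a claim that many such patients will enrol.

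**What to change.** 1. From the medication list in Section 6.2.1 and the Epic and pharmacy records in Section 3.1, code one baseline field: opioid use before surgery, yes or no, for example in the 30 days before surgery. Use only information dated before surgery, so that the block cannot affect the coding.
2. In Section 6.2, prespecify this field as a between-patient baseline factor in the opioid analysis, beside treatment and, where measures are repeated, time. To the extent that users and non-users differ in mean, this removes the p(1−p)d² component from the residual variance.
3. Keep every randomised patient in the long-term use and refill comparisons, and also report these outcomes separately for pre-operative users and non-users, so that new and continuing use can be told apart.

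Leave exclusion 2 as it is. The cost is one coded field, a look at earlier dates in records staff already open, and one model term (one degree of freedom out of 146 evaluable patients). The subgroup of users may be small, so its separate results should be read as descriptive.

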4.3 Vulnerable Subjects

No vulnerable populations will be intentionally solicited. It is possible that employees, economically disadvantaged persons and students will be solicited in the course of enrollment however no one will be specifically recruited for these reasons and no one with ties to the NYU Anesthesiology and Orthopedics department or NYU School of Medicine will be eligible for participation.

4.4 Recruitment and Consent

This study will utilize EPIC to identify subjects and use Redcap in addition to the firewall protected shared drive to manage and store relevant data.

Process of Consent

The consent for participation will be obtained on day of surgery in pre-operative holding room by the regional anesthesiology fellow, Attending Physician, or authorized researcher. Extensive discussion of risks and possible benefits of participation will be provided to the participants and their families. Consent forms will be IRB-approved and the participant will be asked to read and review the document. The investigator will explain the research study to the participant and answer any questions that may arise. All participants will receive a verbal explanation suited to their comprehension of the purposes, procedures, potential risks and their rights as research participants. Participants will have the opportunity to carefully review the written consent form and ask questions prior to signing. The participants will have the opportunity to discuss the study with their surrogates or think about it prior to agreeing to participate. The participant will sign the informed consent document prior to any procedures being done specifically for the study. The participants may withdraw consent at any time throughout the course of the trial. A copy of the signed

CONFIDENTIAL

This material is the property of the NYU School of Medicine and Langone Medical Center. Do not disclose or use except as authorized in writing by the study sponsor

informed consent document will be given to the participants for their records. The rights and welfare of the participants will be protected by emphasizing that the quality of their medical care will not be adversely affected if they decline to participate in this study.

A copy of the signed informed consent document will be given to the patient, placed in the patient's electronic medical record and the original copy will be stored in the research regulatory binder. Any alteration to the standard consent process (e.g. use of a translator, consent from a legally authorized representative, consent document presented orally, etc.) and the justification for such alteration will likewise be documented.

Subject Capacity

All subjects will be assessed for capacity to give informed consent. Capacity will be assessed through the subjects' ability to express understanding of the information presented to them, their ability to express a choice, their appreciation of how this is relevant to them, and reasoning about how the study might impact them and others.

Subject/Representative Comprehension

The subject themselves will have to clearly state back the basic goals of the study (i.e. to look at the effect of different local anesthetics on post op pain after total shoulder replacement surgery) and state that they are willing to participate. This may be done in English or in their primary language with an interpreter.

If a subject requests information regarding opting out of further recruitment for all research, subjects will be directed to contact research coordinator, [name] at [[contact]]([contact]).

4.5 Duration of Study Participation

While the study will be open for 3 years after beginning enrollment, the actual length of a study subject's participation is four weeks.

4.6 Total Number of Participants and Sites

Recruitment will end when approximately 184 participants are enrolled. It is expected that approximately 184 participants will be enrolled in order to produce 146 evaluable participants. The only site for enrollment will be the NYU Langone Orthopedic Hospital.

4.7 Participant Withdrawal or Termination

Participants are free to withdraw from participation in the study at any time upon request. An investigator may terminate participation in the study if:

- Any clinical adverse event (AE), laboratory abnormality, or other medical condition or situation occurs such that continued participation in the study would not be in the best interest of the participant
- The participant meets an exclusion criterion (either newly developed or not previously recognized) that precludes further study participation

4.8 Premature Termination or Suspension of Study

This study may be temporarily suspended or prematurely terminated if there is sufficient reasonable cause. If the study is prematurely terminated or suspended, the PI will promptly inform the IRB and will provide the reason(s) for the termination or suspension.

Circumstances that may warrant termination or suspension include, but are not limited to:

1. Determination of unexpected, significant, or unacceptable risk to participants;
2. Demonstration of efficacy that would warrant stopping;

CONFIDENTIAL

This material is the property of the NYU School of Medicine and Langone Medical Center. Do not disclose or use except as authorized in writing by the study sponsor

3. Insufficient compliance to protocol requirements;
4. Data that are not sufficiently complete and/or evaluable; or
5. Determination of futility

5 Risks and Benefits

5.1 Potential Risks

Bupivacaine used for this study is the standard of care for ISB. Liposomal Bupivacaine (EXPAREL®), a second study drug, has recently been approved by the FDA for use in interscalene blocks.

The potential risks associated with bupivacaine include neurologic and cardiac toxicity, if injected intravascularly. However, the risk is very low because a trained anesthesiologist using ultrasound guidance will perform the nerve block. This allows the anesthesiologist to see and avoid blood vessels when administering the medication. Additionally, the syringe of the local anesthetic will be aspirated prior to injection to ensure that the block needle tip is not intravascular.

The use of Liposomal Bupivacaine or Exparel® in this study is experimental and may cause side effects. Exparel® has recently been approved by the FDA to be used in interscalene blocks. The potential risks associated with Exparel® include nausea, constipation, and fever. In addition, there can be temporary sensory and motor loss, depending on the dosage, site of injection and duration of the nerve block. However, the amount (10mL) used in this study meets FDA dosage-regulations for this medication.

Potential Benefits

Study subjects may experience better pain control, improved satisfaction, decreased need for opioids and reduced incidence of side effects. If the study is not inconclusive, the study's results may benefit future patients by showcasing that Liposomal Bupivacaine improves pain control beyond 24hours in an ISB. Additionally, advocate for the use of Liposomal Bupivacaine as the standard of care for peri- and postoperative pain control in future patients undergoing TSA.

6 Statistical Analysis

